The second secondary outcome checks for **change in the proportion of the population reporting they had had their blood pressure measured**. This will be derived from Question 4 – "Have you ever had your blood pressure measured by a *doctor, nurse or other health workers?*" The third secondary objective is on **change in the proportion of the population reporting that they are using medication for hypertension.** Derived from Question 3 – "Have you received any drugs for high blood pressure prescribed by a doctor, nurse or other health worker in the last two weeks?. These two are direct variables from the questionnaire and do not need any further computation. For the primary analysis of this outcome, only those who name specific drugs will be categorized as being prescribed drugs for high blood pressure.

The fourth is change in the proportion of the population at different levels of bloodpressure-related cardiovascular risk by age group and sex. In this case we will also need **blood-pressure-related cardiovascular risk** divided into the different levels of no added risk, low added risk, moderate added risk and high added risk (see Table 2).

The secondary objectives under section 2.2.2, e and f (restated below) do not need any additional computations, and will be derived from clinic link data. These two outcomes are:

- e) Change in the proportion of people in the population recorded as having attended a clinic in the last year.
- f) Retention in care of people with diagnosed hypertension defined by the proportion of appointments kept during the study period.

Note that the clinic link data will provide information on the proportion of people recorded as having attended a clinic in the last year, rather than, as originally stated, reporting they had attended.

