6 ANALYSIS OF PRIMARY OUTCOME

6.1 Definition of outcome measure

The primary outcome will be the change in the percentage of people in the population who have elevated blood pressure that is combined with other factors resulting in a risk profile that indicates moderate or greater added risk of cardiovascular disease. as indicated by the shaded cells in Table 2. This includes individuals with either: a systolic blood pressure of 160 and above, diastolic of 100 and above, systolic blood pressure of 140-159 plus one or more risk factors, or diastolic blood pressure 90-99 plus one or more risk factors. These data will be obtained from two population surveys (one before the start of the trial and one after the trial ends).

Table 2. Modified South African Guideline: Stratification of cardiovascular risk in patients with hypertension (defined as SBP>139 or DBP>89)

Blood pressure (mmHg)	Presence of risk factors or other conditions						
	No risk factors	One or two risk factors	Three or more risk factors or diabetes	Associated clinical conditions			
SBP 140 -159 or DBP 90-99	Low Added Risk	Moderate Added Risk	High Added Risk	Very High Added Risk			
SBP 160 -179 or DBP 100-109	Moderate Added Risk	Moderate Added Risk	High Added Risk	Very High Added Risk			
SBP 180 + or DBP 110+	High Added Risk	Very High Added Risk	Very High Added Risk	Very High Added Risk			

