The definition of diabetes can come either from a recorded high blood sugar or a record of being on treatment for diabetes. So someone has diabetes i f their blood sugar in Q34(?) > 11.1 mmol/L OR • if they have answered 'yes' to Q 4,5 and 6 • and are using one of the drugs listed in questions 6a, b, or c. The person needs to have been told they have diabetes, AND have taken medicine for it in the last two weeks AND the medicine should be one of those listed in Q6a (if it is an 'other drug' then [name] and I will need to make a decision about it). */ gen Q6a_GI i bencl ami de_bi n=(Q6a_GI i bencl ami de<=2) gen Q6a_Gl i cl azi de_bi n=(Q6a_Gl i cl azi de<=2) gen Q6a_Metformi n_bi n=(Q6a_Metformi n<=2) gen Q6_drugs_taken= Q6a_GI i bencl ami de_bi n+Q6a_GI i cl azi de_bi n+Q6a_Metformi n_bi n gen di abetes=(Q35_Gl ucosel nBl ood>11.1 & Q35_Gl ucosel nBl ood! =.) | (Q5_Rai sedBl oodSugar==1 & Q6_drugs_taken>=1) *To calculate mean systolic blood pressure, the first systolic reading will be discarded and then the mean systolic pressure will be calculated as the mean of the second and third readings. The mean diastolic blood pressure and pulse will be similarly calculated. Participants will be grouped according to blood pressure level: 4:Stage two plus hypertension: systolic >180 and/or diastolic >110 3: Stage two hypertension: systolic > 160 and <180 and/or diastolic >100 and <110 2: Stage one hypertension: systolic > 140 and <160 and/or diastolic >90 and <99 1: Normal blood pressure systolic < 140 and diastolic < 90 */ , gen systolic_bp_mean= 0.5*(028a_Systolic2+029a_Systolic3) gen diastolic_bp_mean= 0.5*(028b_Diastolic2+ 029b_Diastolic3) gen heart_rate_mean= 0.5*(028c_HeartRate2+ 029c_HeartRate3) gen bplevel =. replace bplevel=1 if systolic_bp_mean<140 & diastolic_bp_mean<90 replace bplevel=2 if (systolic_bp_mean>=140 & systolic_bp_mean< systolic_bp_mean<160) | (diastolic_bp_mean>=90 & diastolic_bp_mean<100) (diastoirc_pp_mean>=90 & diastoirc_pp_mean<100)
 replace bplevel=3 if (systolic_bp_mean>=160 & systolic_bp_mean<180) |
 (diastolic_bp_mean>=100 & diastolic_bp_mean<110)
 replace bplevel=4 if (systolic_bp_mean>=180 & systolic_bp_mean!=.) |
 (diastolic_bp_mean>=110 & diastolic_bp_mean!=.)
 label define bplabel 1 "Normal blood pressure" 2 "Stage One hypertension"

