 3 "Stage Two hypertension" 4 "Stage Two Plus hypertension" label values bplevel bplabel Creation of the minor cvd risk factors variable gen minor_cvd_riskfactors=waist+family_risk+dyslipedemia+smoking+AgeRiskGroup replace minor=. if QOa_InterviewOutcome>2 * Creation of Stroke, Heart Failure and Heart Attack variables gen_stroke_ever=(Q7_EverHadStroke==1 & Q7_EverHadStroke!=. | Q8_EverRecei veStrokeRx==1 & Q8_EverRecei veStrokeRx!=.) gen heart_failure=(Q10_HeartFailure==1 & Q10_HeartFailure!=. | Q11_Recei vedHeartFai I ureRx==1 & Q11_Recei vedHeartFai I ureRx!=.) gen attack_heart=(Q16_HeartAttack==1 & Q16_HeartAttack~=.| Q17_Recei vedHeartAttackRx==1 & Q17_Recei vedHeartAttackRx~=.) * Creation of the associated clinical factors variable gen associated_clinical_factors= stroke_ever+heart_failure+attack_heart

Page 31 of 32

replace associated=. if QOa_InterviewOutcome>2 *Table Two Analysis plan codes gen riskfactors_category=. replace riskfactors=1 if minor_cvd_riskfactors==0 replace riskfactors=2 if minor_cvd_riskfactors>=1 & mi nor_cvd_ri skfactors<=2</pre> replace riskfactors=3 if minor_cvd_riskfactors>=3 & minor_cvd_riskfactors!=. | diabetes==1
replace riskfactors=4 if associated_clinical_factors>=1 & associated_clinical_factors!=. label define risk 1 "No risk factors" 2 "One or two risk factors" 3 "Three or more risk factors or diabetes" 4 "Associated clinical conditions" label values risk risk tab bplevel risk, set type double gen cvdnkateko=. replace cvdnkateko=0 if bplevel==1 | minor_cvd_riskfactors==0 & bplevel!=. replace cvdnkateko=1 if bplevel ==1 & minor_cvd_riskfactors==0 & associ ated_cl i ni cal _factors==0
 repl ace cvdnkateko=2 if (bpl evel ==2 & mi nor_cvd_ri skfactors>=1) & (bpl evel == 2 & mi nor_cvd_ri skfactors<= 2) /// |(bpl evel ==3 & mi nor_cvd_ri skfactors==0)| (bpl evel ==3 & mi nor_cvd_ri skfactors>=1) & (bpl evel ==3 & mi nor_cvd_ri skfactors<=2) repl ace_cvdnkateko=3 if (bpl evel ==2 & mi nor_cvd_ri skfactors>=3 & minor_cvd_riskfactors!=.) /// associated_clinical_factors>=1 & associated_clinical_factors!=.) /// |(bpl evel ==4 & minor_cvd_riskfactors>=1 & minor_cvd_riskfactors<=2)| (bpl evel ==4 & minor_cvd_riskfactors>=3 & minor_cvd_riskfactors!=.) label var cvdnkateko "Levels of CVD Risk Modified SA2015 Nkateko" label define cvdnkateko 0 "No risk" 1 "Low risk" 2 "Moderate risk" 3 "High risk" 4 "Very high risk"

label values cvdnkateko cvdnkateko

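### Appendix C codes normal blood pressure without risk factors as low risk and stage-one hypertension without risk factors as no risk, so the No risk and Low risk rows of Table 9 would hold the wrong people

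*SAP*

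**What the plan says.** Section 5.7 of the SAP says that secondary outcome d needs blood-pressure-related risk "divided into the different levels of no added risk, low added risk, moderate added risk and high added risk", and refers to Table 2 for the levels. Table 2 (section 6.1) covers only people with SBP above 139 or DBP above 89. Its first cell, stage-one pressure with no risk factors, reads "SBP 140 -159 or DBP 90-99 Low Added Risk". Appendix Table 4 repeats this.

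Appendix C builds the variable `cvdnkateko`, in which 0 is labelled no risk and 1 low risk. Normal pressure is set by "replace bplevel=1 if systolic_bp_mean<140 & diastolic_bp_mean<90", and `bplevel` 2 is stage-one hypertension. Two lines then decide the lowest levels:

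- Level 0: "replace cvdnkateko=0 if bplevel==1 | minor_cvd_riskfactors==0 & bplevel", where the last term requires `bplevel` not to be missing.
- Level 1: "replace cvdnkateko=1 if bplevel ==1 & minor_cvd_riskfactors==0", with the further condition that the count of associated clinical conditions is zero.

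Table 9 in Appendix B reports No risk and Low risk as separate rows, each with within-arm change, a between-arm test and p-values, and asks for repeats by sex.

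**The concern.** The level-1 line is keyed to normal pressure, whereas Table 2 keeps low added risk for stage-one pressure without risk factors. As printed, the only people who can be labelled low risk are normotensives with no risk factor and no associated condition. Normotensives who do have risk factors are labelled no risk, so acquiring a risk factor lowers the label. The people whom Table 2 calls low risk are never labelled so.

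The direction of the reported change is also at stake. Section 3.1 states that the trial aims to reduce blood pressure. If fewer people without risk factors are at stage one and more are normal at the second survey, Table 9 would show a move out of No risk and into Low risk. An improvement at this boundary would read as a deterioration.

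**Working it through.** No formula applies; the check is a trace of the code against Table 2.

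**Inputs.** The `bplevel` definitions, the `cvdnkateko` assignment lines and the value labels come from Appendix C. The target classes come from Table 2 (section 6.1) and Appendix Table 4. Stata evaluates `&` before `|`, so the level-0 line reads: normal pressure, or else zero minor factors with known pressure.

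**Trace of the lowest cells**

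| Blood pressure | Minor factors | Associated condition | After level-0 line | After level-1 line | Table 2 |
|---|---|---|---|---|---|
| Normal (1) | 0 | none | 0 | 1, low risk | outside the table, so no added risk by implication |
| Normal (1) | 1 or more | none | 0 | 0, no risk | outside the table, so no added risk by implication |
| Normal (1) | 0 | present | 0 | 0, no risk | outside the table, so no added risk by implication |
| Stage one (2) | 0 | none | 0 | 0, no risk | "Low Added Risk" |

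**Do later lines repair this?** The level-2 line takes stage one only with one or two minor factors. The legible part of the level-3 line takes it with three or more. No legible line assigns level 1 again, or moves stage one with no factor and no associated condition away from 0.

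**Effect of re-keying.** The legible lines were run for every combination of `bplevel` 1 to 4, minor factors 0 to 3 and associated condition absent or present: 4 × 4 × 2 = 32 cells. They were run as printed and again with only the level-1 line changed to `bplevel==2`. Exactly two cells differ:

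- normal pressure, no factor, no associated condition: low risk becomes no risk;
- stage one, no factor, no associated condition: no risk becomes low risk, as in Table 2.

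No cell crosses the boundary between low and moderate risk. Diabetes was not a dimension of this run, because no legible `cvdnkateko` line uses it.

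**Which outputs change.** Of the seven rows of Table 9, two change: No risk and Low risk. The combined No or low row does not, because both cells stay within it. Tables 5 to 8 cross blood pressure with risk-factor category and do not need `cvdnkateko`.

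**The case against.** The strongest reply is that section 5.7 and the title of Appendix C offer this code for the primary outcome, and for that purpose the line is harmless. The written rule for risk levels is right: section 5.7 refers to Table 2, and Appendix B says to allocate people using Table 4. On this view it is a coding slip that any cross-tabulation would expose. Much of that stands, and it limits the weight of the point. But `cvdnkateko` carries all five risk labels and is the only code printed for the levels in Table 9, so the slip would pass into a prespecified secondary result unless someone looked for it.

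A second reply is that Table 2 has no row for normal pressure, so the code contradicts it literally only in the stage-one cell. That is correct. For normotensives the conflict rests on the table's restriction to hypertension and on Table 9 having its own No risk row.

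Two stronger readings are tempting. A reader might infer that the primary outcome, or the whole of secondary outcome d, is wrong. The trace does not support this: levels 0 and 1 both lie below moderate, and the other rows and Tables 5 to 8 do not depend on this line. A reader might also infer that the code leaves some higher-risk cells at 0, for example the highest pressure category with no minor factors. Part of the code for levels 3 and 4 is not legible in the text reviewed, so nothing can be concluded about those cells.

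**Conclusion.** The code contradicts Table 2 and Appendix Table 4 for stage-one hypertension without risk factors and, by implication, for normal blood pressure without risk factors. The consequence is confined to the separate No risk and Low risk rows of Table 9 and their repeats for men and women.

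Within those rows the error is complete for the cell concerned: on the legible code, nobody in the low-added-risk cell of Table 2 is labelled low risk. The number of people misplaced cannot be derived from the documents. Section 3.5 plans on 36% at moderate or greater risk, so 100% − 36% = 64% would fall in the two rows together. That is a ceiling and not an estimate, because the split by blood pressure and risk factors is not given.

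The conclusion rests on the two assignment lines being printed as intended, and on no unreadable later line reassigning these cells. Neither line shows damage, although other parts of the appendix do.

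**What to change.** Leave the level-0 line as it is and re-key the level-1 condition to:

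`bplevel==2 & minor_cvd_riskfactors==0 & diabetes==0 & associated_clinical_factors==0`

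All normal blood pressure then stays at 0. The diabetes term is needed because Table 2 puts diabetes in a higher-risk column.

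Do not shorten the level-0 line to normal pressure alone. On the legible code, stage one with diabetes but no minor factor, and the highest pressure category with no minor factor, would then go from 0 to missing. Because the main analysis uses complete cases (section 5.5), that could remove people from the primary outcome.

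Then cross-tabulate `cvdnkateko`, including missing values, against `bplevel` by `riskfactors_category`. Confirm that every hypertensive cell equals Table 2, that all normal pressure is at 0, and that nobody with complete data is missing or left at 0 in error. The cost is one changed line and one check table, with no new data and no change to the primary analysis.
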